## SYNOPSIS

Title	Molecular pathways involved in knee pain: an observational study
Short title	Molecular pathways involved in knee pain
Chief Investigator	[name] [name]
Objectives	
Observational Study:
 
[1] To test whether there is an association between proteomic concentrations in the synovial fluid and pain hypersensitivity.
 
[2] To identify proteomic signatures in synovial fluid of centrally vs peripherally driven knee pain.
 
[3] To investigate the relationship of pain hypersensitivity and different proteomic profiles with radiologically-established joint structural changes and muscle strength.
 
[4] To explore the correlation between knee inflammation (effusion, synovial hypertrophy or/and synovial hyper vascularity) and biomarkers of insulin resistance, stress, DNA markers, poor metabolism and knee pain.

Study Configuration	Observational cross-sectional study
Setting	University and secondary care
Sample size estimate	
Observational Study: We propose to compare proteomic signatures in 140 knee pain cases. To achieve a Bonferroni <math>p < 1.25 \times 10^{-5}</math> (adjusting for 4000 tests, i.e. the number of proteins in the Somalogic platform) effect sizes of <math>\beta=0.64</math> in units of standard deviations are needed to achieve 80% statistical power. Based on the effects seen on radiographic progression (standardized <math>\beta=0.62</math>) these effects appear reasonable and achievable with the proposed sample size.
 
Reliability Sub-study: Considering that the study will comprise two different sessions (<math>n=2</math>) featuring one measurement within each and with minimally accepted reliability of <math>p_0=0.5</math> and expected reliability of <math>p=0.8</math>, the minimum sample size has been calculated to be 22 participants. High variability is not expected however, to account for such an occurrence, data will be collected from 25 individuals.

Number of participants	Observational Study: 140 Sub-study: 25
Eligibility criteria	
Inclusion criteria:
 
 
• have the ability to give informed consent
 
• be 45 years or over
 

	
 
have complaints of knee pain for 3-6 months with or without radiographically established OA (K/L scale score <math>\geq 1</math>)
 
have complaints of knee pain for 3-6 months with or without satisfying the non-radiographic American College of Rheumatology criteria for knee OA
 
are willing to undertake knee synovial fluid aspiration
 
be able to speak, read, and write in English as all instructions and questionnaires are designed in the English language
 
 
Exclusion criteria:
 
 
Inability to give informed consent due to cognitive impairment or otherwise – (capacity levels are already established under GP care)
 
Inability to understand key aspects of the study due to cognitive impairment or otherwise
 
Giving history of additional co-morbidities such as cancer, neurological conditions, inflammatory joint diseases including rheumatoid arthritis, diabetic neuropathies, fractures or other conditions causing greater disability than their knee pain
 
Acute soft tissue injury to the knee within last 3 months before potential recruitment
 
 
Same criteria apply for the sub-study

Description of interventions	Clinical assessment for this study will include self-report questionnaires, and ultra-sound scanning, synovial fluid aspiration, blood samples, and faecal extraction as well as balance and muscle strength assessment through a sensitive platform and an isokinetic dynamometer respectively. The duration of the clinical assessment will be approximately 1.5 hours.
Duration of study	18 months Planned recruitment date: January 2020 Per participant appointment duration (Observational and Sub-study): 1 x 2 hours
Outcome measures	
Primary: Pain measured by patient reported pain scoring.
 
Secondary: Knee joint morphology on X-ray, Central aspects of pain in knee (CAP-Knee), Synovial fluid protein concentration, Cognitive function (CFQ), Frailty (FRAIL), Inflammatory markers on ultrasound (Synovial fluid, synovial hypertrophy and hypervascularity), Muscle Strength, , Biomarkers of insulin resistance, DNA markers, compromised metabolism, and stress generators (cortisol, gut microbiota), Physical functioning (Time up and go test, 30-second sit to stand test), Western Ontario and McMaster Universities Osteoarthritis Index (WOMAC), General health questionnaire (EQ5D-5L)

Statistical methods	Standard parametric regression methods will be used to assess the levels of association between proteomic profiles, pain and inflammatory markers on ultrasound.

## ABBREVIATIONS

VA	versus Arthritis
CAP-Knee	Central Aspects of Pain in the Knee
CFCF	Consent for Contact Form
CFQ	Cognitive Failures Questionnaire
CI	Chief Investigator overall
CNS	Central Nervous System
CPA	Computerised Pressure Algometer
CS	Central Sensitisation
CSB	Clinical Sciences Building
cmRCT	Cohort Multiple Randomised Controlled Trial
CPM	Conditioned Pain Modulation
DAP	Data Analysis Plan
DCU	Data Collection Unit
FFQ	Food Frequency Questionnaire
FRAIL	Simple Frailty Questionnaire
GCP	Good Clinical Practice
GP	General Practitioner
HADS	Hospital Anxiety and Depression Scale
ICC	Intraclass Correlation Coefficient
ICF	Informed Consent Form
ICOAP	Intermittent and Constant Osteoarthritis Pain
JA	Joint Academy
K/L	Kellgren and Lawrence system for classification of osteoarthritis of knee
KPIC	Knee Pain in the Community
MLR	Multiple Linear Regression
MSK	Musculoskeletal
MSK-HQ	The Versus Arthritis Musculoskeletal Health Questionnaire
MSK-USS	Musculoskeletal Ultrasound Scan
MVC	Maximum Voluntary Contraction
NHS	National Health Service
NRS	Numerical Rating Scale
NUH	Nottingham University Hospital Trust
OA	Osteoarthritis
PA	Posterior-Anterior
PIS	Participant Information Sheet
PPI	Patient and Public Involvement
PPT	Pressure Pain Threshold
PRU	Patient Response Unit
QST	Quantitative Sensory Testing
REC	Research Ethics Committee
R&D	Research and Development department
SAE	Serious Adverse Event
SF	Synovial fluid
TS	Temporal Summation
TUG	Time Up and Go Test
USGA	Ultrasound-guided Aspiration
WOMAC	Western Ontario and McMaster Universities Osteoarthritis Index
30CST	30-second Sit to Stand Test

## STUDY BACKGROUND INFORMATION AND RATIONALE

Osteoarthritis (OA) is the most common cause of disability in the elderly population and most individuals suffering from osteoarthritis are managed in the primary care setting (1). Knee OA is the most common form of arthritis and the most common cause of knee pain in the world (2). The rate of knee arthritis is as high as that of cardiac disease and is the most common problem in individuals over the age of 65 (3). In the United Kingdom, 10% of 65 to 74-year-old individuals consult their general practitioners about OA per year (4). Out of the entire population, 4% attend their general practitioners as a result of knee OA, and half of them (2%) consult their general practitioner for the first time or with the acute flare of knee arthritis (1).

We will recruit 140 individuals with OA-related knee pain, and we will record their pain levels on the Numerical rating scale (NRS) at a single time-point. The validity and sensitivity of NRS have been established numerous times (14-18).

Metabolic evidence from body secretions can provide significant insight about the course of OA, as the presence of glucosamine and chondroitin sulfate in faecal samples has shown to improve the symptoms of the condition and delay its progression (56). Nutritional information and metabolic evidence from faecal samples can be used to explore associations of gut microbiota with pain sensitivity and stress levels (57, 58).

The widely utilised Western Ontario and McMaster Universities Osteoarthritis Index (WOMAC) will be also used for the evaluation of knee OA. It is a self-administered questionnaire made of 24 items and consists of three subscales covering pain, stiffness and physical function. It has been used extensively and is considered a valid and reliable tool (59-63). Frailty has been also found to be a predictor of disability (66) and a determinant of treatment outcomes (67-69) and the Simple Frailty Questionnaire (FRAIL) is considered a valid and reliable tool for that purpose (70).

Both the 30-second sit to stand test (30CST) and the 'time up and go' (TUG) test will be used to see if patients have improved their lower limb fitness levels. 30CST has shown excellent reliability and validity (63, 71, 72). TUG has been widely used in clinical setups and is a valid tool to assess necessary functional mobility (73-79).

Musculoskeletal Ultrasound scan (MSK-USS) will be also conducted on the knees of participants to establish if they have inflammation of the synovial membrane. There is enough evidence that inflammation is present in all stages of OA (108-111). Synovitis or inflammation of synovial fluid is associated with pain, disease severity and, OA progression (108, 112). Synovitis manifests as synovial membrane thickening, increased vascularity, and/or joint effusion (108, 113-115). During MSK-USS, the presence of synovial fluid, synovium hypertrophy, and Power Doppler will be also assessed. Synovial hypertrophy, synovitis and knee effusion are linked with arthritis in the knee and associated with knee pain in osteoarthritis (116-121). Power Doppler provides a reliable and accurate method for visualising blood flow in the synovial tissue, and histological findings support the value of this technique (119, 122, 123). An ultrasound scan is considered to be a valid and reliable instrument for the assessment of synovial disease (113, 119, 120, 124) and synovitis is strongly associated with osteoarthritis as mentioned earlier. The synovial fluid will be aspirated (subject to participant consent), in order to establish a phenotype which is strongly associated with OA. Studying synovial fluid biomarkers alongside clinical, radiographic and ultra-sonographic characteristics is one strategy to improve resolution and stratification into targetable OA phenotypes (125). Synovial fluid aspiration will be ultrasound guided as it increases the accuracy of needle placement

compared to blind needling (95.8% versus 77.8%,  $p < 0.001$ ) (126) reduces procedural pain by 43%, improves effusion detection by 200%, and volume of synovial fluid aspirated by 337% compared with blind synovial fluid aspiration (127). Ultrasound guidance also reduces procedural pain (43% reduction) in knees with no palpable effusion and increases the responder rate and therapeutic duration by 107% and 36% respectively (128-132).

Optionally, isometric quadriceps strength will be also assessed to establish current strength levels of vastus medialis muscle and see whether muscle strength associates with centrally driven pain or proteomic synovial concentrations. Quadriceps muscles strength deficits are associated with knee osteoarthritis (133). Isometric testing will be done at 30 and 60 degrees of flexion as per the protocol of a previous study (134). Hand grip strength will also be measured as an option

Blood samples will be also extracted to assess the biomarkers (including serum levels and gene expression levels of various molecules) and to establish insulin resistance (135, 136).

Collection and study of these parameters can provide more insight into the traits of knee pain, allow the examination of possible correlations to each other, and highlight potential detrimental effects of them on knee joint health.

## **STUDY OBJECTIVES AND PURPOSE**

### **PURPOSE**

The primary purpose of this study is to explore the potential molecular links between pain and structure on knee pain using synovial fluid proteomics. A secondary purpose is to explore the association of knee pain with biomarkers of stress and metabolism

### **HYPOTHESIS**

Among individuals with moderate to severe knee pain different proteomic signatures will be seen in synovial fluid of the affected knees.

### **PRIMARY OBJECTIVE**

1. To identify proteomic signatures in synovial fluid of the knee joint in individuals with knee pain.

### **SECONDARY OBJECTIVES**

1. To test whether there is an association between proteomic concentrations in the synovial fluid and pain.
2. To link the changes in pain and physical activity to biomarkers of insulin resistance, stress, poor metabolism, inflammation and pain.
3. To investigate the relationship of pain and different proteomic profiles with radiologically-established joint structural changes and muscle strength.
4. To explore the correlation between knee inflammation (effusion, synovial hypertrophy or/and synovial hyper vascular), biomarkers of insulin resistance, DNA markers, stress, poor metabolism, gene expression and knee pain.

### **DETAILS OF PRODUCTS**

We will be using ultrasound to assess participant knee joints.

#### Ultrasound:

An ultrasound will be used to image both knee joints using a Toshiba Aplio SSA-770A machine with a multi-frequency (7 – 12 Hz). This equipment belongs to the university and is CE marked.

### **Known Side Effects**

There are not any known side effects from ultrasound. There can be a small amount of pain from the aspiration site.

## STUDY DESIGN

### Study Configuration

A single-centre observational cross-sectional study in a university and hospital setting with participants suffering from knee pain.

### Primary endpoint

The primary outcome measure is pain measured by patient reported scores.

### Secondary endpoint

- Synovial fluid protein concentration (synovial fluid)
- Knee joint morphology on X-ray
- Central aspects of knee pain (CAP-Knee)
- Inflammatory markers on ultrasound (Synovial fluid, synovial hypertrophy and hypervascularity)
- Muscle Strength (Dynamometer)
- Balance (Balance platform)
- Biomarkers of insulin resistance (blood, urine) and metabolic rate (faeces)
- Gene expression levels of molecules in pain
- Physical functioning (Time up and go test, 30-second sit to stand test)
- Western Ontario and McMaster Universities Osteoarthritis Index (WOMAC)
- General health questionnaire (EQ5D-5L)

All these endpoints will be measured at a single time-point (baseline) and at a follow up time point 120 days for those who subsequently go on to have surgery

### Stopping rules and discontinuation

As the study involves only a single clinical assessment and does not involve investigational medicinal products or medical devices it is not envisaged that circumstances will arise that require termination or discontinuation of this study.

### Study Management

The study will be managed in Academic Rheumatology, Clinical Sciences Building by the Research Manager under the supervision of the Chief Investigator who has overall responsibility for the study and shall oversee all study management.

Other members of the team are [name] (Director of Pain Centre Versus Arthritis (VA)), [name] (Research Metrologist), [name] (Post-doctorate Research Fellow), [name] (Post-doctorate Research Fellow) and [name] (Musculoskeletal Project Manager). [name] (Professor of Orthopaedic Surgery) will provide oversight of research procedures conducted within NHS facilities. [name] (Consultant Orthopaedic Surgeon) will facilitate recruitment from NHS waiting lists. [name] (NUH Orthopaedic Clinical Research Manager) will support recruitment and research delivery from NHS areas.

The study management group will meet regularly and have documented quarterly meetings from the start of the study. The group will also monitor and supervise the progress of the study

and advice on recruitment rate and unforeseen logistical issues to ensure that its objectives are achieved.

The data custodian will be the CI who will also have overall responsibility for the study and shall oversee all study management.

## **Duration of the Study and Participant Involvement**

### **Study Duration and Schedule of Events:**

The trial is expected to start in April 2020, and enrolment will end in the late summer of 2022. After about two months from the end of recruitment, all data will be put together for coding and further processing. Data analysis will be performed by a co-investigator supervised by the CI.

### **Participant Duration:**

Those individuals who agree to participate will be asked to attend one session, at a time of their convenience in order to receive all relevant examination and samples extraction

Therefore, in total, individuals will be asked to attend a single session for no more than 2 hours.

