Study visits will take place either in the Clinical Sciences Building in Academic Rheumatology, or in an NHS clinic room at the Queens Medical Centre site. Participants who satisfy the eligibility criteria upon the telephone screening will be invited to attend a study visit, at a day of their convenience. That visit will be considered as their single study session. The purpose of the visit will be to further establish suitability and gain full consent about knee aspiration and all other proceedings (samples, ultrasound, functional assessment) before any study activities are undertaken. Participants will be eligible for inclusion to the study if they are willing to undergo knee synovial fluid aspiration and demonstrate radiographic evidence of osteoarthritis (K/L= 1 or above) or if they satisfy the American College of Rheumatology clinical criteria for knee OA (139) even in the absence of radiographic findings (e.g. knee pain and three or more of the following: over the age of 50, less than 30 minutes of stiffness in the morning, no palpable warmth on synovium, bony tenderness, bony enlargement, crepitus on active motion).

Participants will be free to leave the study at any time without giving any reason. Participants who indicate in their questionnaire that they are willing to receive information about future knee pain studies may withdraw this indication at any time, and this will be altered appropriately on the study database. Participants will be made aware via the questionnaire that all data will remain confidential and will be anonymised before use in further analysis.

It will be explained to the potential participant that entry into the study is entirely voluntary and that their treatment and care will not be affected by their decision. It will also be explained that they can withdraw at any time, but attempts will be made to avoid this occurrence. In the event of their withdrawal, it will be explained that any data collected so far cannot be erased, and we will seek consent to use the data in the final analyses where appropriate (via the information sheet and consent form). Those who withdraw from the study will be made aware that this will not in any way affect their future care.

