## **Study Regimen**

Participants seeking care for their knee pain will be informed of the study both orally and in writing. Those who qualify for the study will be asked to come to Academic Rheumatology for a single session. All research activities will be undertaken on the same session which is expected to last no longer than 2 hours. During the single session, participants will sign the informed consent form (ICF) and will be asked to go through the study procedure. All participants will have blood samples extracted. All participants will have a knee ultrasound scan by a trained member of the study team to assess their knee and locate the best needle insertion point and go through the ultrasound-guided aspiration (USGA) procedure. Participants will then have their pain sensitivity, strength, balance and function measured by special tests (sit to stand, time up and go). Outcome measures about pain mechanisms (CAP-Knee), OA (WOMAC), cognitive function (CFQ), frailty (FRAIL), and health (EQ5d-5L) will be completed by participants at home online or on paper copies. Participants will be also asked if they wish to donate a faecal sample and if they agree they will be given a collection kit to take home along which will be shipped back by post.

To summarise, the total study duration, including recruitment and the assessment visit, will be 18 months. The key stages are detailed below:

- Individuals who agree to attend for a clinical assessment will participate for a single appointment. This appointment will last approximately 2 hours.
- They will be seen at the Academic Rheumatology Unit, Clinical Sciences Building, Nottingham City Hospital or in an NHS clinic room at Queens Medical Centre.
- Transport (taxi) will be arranged if required and any travel expense will be reimbursed.
- Our Research Nurses will get a 15ml blood sample from the participant
- Once blood samples have been collected participants may be offered a light breakfast and drink refreshment before a brief assessment to confirm medical history and current medications.
- Questionnaires such as WOMAC, EQ5D-5L, CFQ, CAP-Knee, FRAIL and Numeric VAS will be collected.
- Physiological measurements such as 30 seconds sit to stand (30CST), time up and go (TUG), balance and muscle strength assessments will be taken at this point.
- Diagnostic ultrasound of the most painful knee will be conducted and ultrasound guided synovial fluid aspiration will follow.

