### **Laboratory Analysis**

Whole blood may be sent to a specialist company for total genomic DNA extraction and processing using standard protocols. The DNA will be used to identify genes that identify with pain progression and severity. Bacterial DNA will be extracted from faecal samples to identify bacterial lineages associated with pain and inflammation. Cortisol will be extracted from saliva samples. Protein and inflammatory markers will be extracted from urine samples. Faecal samples will be stored until all samples are collected (as this is optional) and then they will be sent to the laboratory. Similarly, biochemical/biomarker analyses may be undertaken by other academic or commercial groups. Such investigations will be undertaken on anonymised samples under usual Material Transfer Agreement arrangements. The study will be registered with the Human Tissue Management Group of the UoN. Storage of these tissues will be managed, transported and handled according to Standard Operating Procedure (SOP) HTMG 004. All shipments will contain a complete inventory of all samples, along with the name of the person responsible for sending the samples. Companies which will be used for the analysis should process the samples within seven days upon receipt or companies with HTA licence will be considered. It is anticipated that samples will be destroyed following analysis. There is no plan for long-term storage of such samples by those companies and no samples are expected to be transported back to UoN.

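### Sampling time and recent food are neither fixed, recorded nor adjusted for, so the exploratory cortisol and insulin-resistance associations with pain may be diluted

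*Combined protocol and SAP*

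**What the plan says.** **Scheduling.** Participant Duration says that participants will "attend one session, at a time of their convenience in order to receive all relevant examination and samples extraction". Recruitment says that those who pass telephone screening "will be invited to attend a study visit, at a day of their convenience". Neither section sets a window by time of day. Study Regimen places all research activities in that one session.

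**Blood.** The collection instruction gives only a volume: "Our Research Nurses will get a 15ml blood sample from the participant". The one line bearing on fasting follows it: "Once blood samples have been collected participants may be offered a light breakfast and drink refreshment".

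**Saliva.** Laboratory Analysis states that "Cortisol will be extracted from saliva samples". Saliva also appears under Transport and Storage of the Tissues, as a sample type that may be left over. The visit steps in Study Regimen do not include collecting it.

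**Use of the markers.** The Synopsis lists "stress generators (cortisol, gut microbiota" among secondary outcomes. The Secondary endpoint section lists "Biomarkers of insulin resistance (blood, urine) and metabolic rate (faeces". Secondary objective 4 explores how knee inflammation relates to "biomarkers of insulin resistance, DNA markers, stress, poor metabolism, gene expression and knee pain". Secondary objective 2 also links insulin-resistance and stress markers to pain.

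**Analysis.** Under Statistics, Methods, the plan is unadjusted Pearson or Spearman correlation, linear regression, and then multiple regression by backward stepwise selection. No term for sampling time or fasting state is named.

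**The concern.** Cortisol varies over the day, and markers such as insulin and glucose change after eating. If some participants are sampled fasted in the morning and others fed in the afternoon, part of the spread in these markers reflects when the visit took place and not the person. Under the planned unadjusted analysis that spread is noise, and it pulls any true association with pain towards zero.

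A second and different problem would arise if visit timing were itself related to pain, for example through recruitment route (community databases or arthroplasty waiting lists) or visit location (Clinical Sciences Building or an NHS clinic room at Queens Medical Centre). Timing could then create an association where none exists.

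Clock time and last food cannot be reliably reconstructed long after a sample is taken. If neither is recorded, a null or a positive finding for these markers could not later be separated from a timing effect.

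**Working it through.** **Step 1: is there any rule?** The sections compare as follows.

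- Participant Duration and Recruitment: time and day are left to the participant.
- Study Regimen: blood comes first and food may follow. This fits a fasted morning visit, but it instructs nobody to fast and does not limit visits to mornings.
- Laboratory Analysis: saliva is assayed for cortisol, with no collection time, number of samples or time since waking.
- Methods: no covariate for time or fasting.

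A fasted morning blood draw is therefore implied, but it is not required, recorded, adjusted for, or reconciled with the scheduling text. For saliva nothing is implied either way.

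**Step 2: is there a plan figure to reproduce?** No. The only power statement concerns the proteomic tests. The documents give no SD, effect size or power for cortisol or insulin-resistance markers, so everything below is illustration.

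**Step 3: dilution.** Inputs:

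- n = 140, from Sample size and justification.
- r = 0.30, the true marker–pain correlation: assumed.
- f = 0.10 to 0.50, the share of marker variance due to timing and unrelated to pain: assumed.
- Two-sided 5% level: assumed.

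Formulas: r_obs = r × √(1 − f); power = Φ(atanh(r_obs) × √(n − 3) − 1.96), with √137 = 11.70. The equivalent sample size is about 140 × (1 − f).

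| f | r_obs | Power at n=140 | Equivalent n | n for 80% power |
|---|---|---|---|---|
| 0 | 0.300 | 95.2% | 140 | 85 |
| 0.10 | 0.285 | 92.9% | 126 | 95 |
| 0.30 | 0.251 | 85.1% | 98 | 123 |
| 0.50 | 0.212 | 71.3% | 70 | 173 |

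For example, at f = 0.50: 0.30 × √0.5 = 0.212; atanh(0.212) = 0.215; 0.215 × 11.70 − 1.96 = 0.56; Φ(0.56) = 0.71.

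The result depends on the assumed r. With r = 0.25, power falls from 84.8% (f = 0) to 80.8%, 70.0% and 55.2% for f = 0.10, 0.30 and 0.50.

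**Step 4: confounding, only if its condition holds.** Let g be the correlation between visit timing and pain, with no true marker–pain association. The spurious correlation is g × √f.

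- If g = 0, it is zero and the false-positive rate stays at 5%.
- If g = 0.2 (assumed), it is 0.063, 0.110 and 0.141 for f = 0.10, 0.30 and 0.50, and the nominal 5% rate becomes 11.5%, 25.1% and 38.5%.

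The documents give no value for g.

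**The case against.** The strongest reply is that the breakfast line points to a fasted morning draw, and that letting participants choose a convenient slot does not rule out choosing among mornings. Fasting instructions may also stand in the participant information sheet or invitation letter, which are not in the reviewed text. Both points have weight. A reader might infer that the plan makes no provision at all for fasting blood; the documents do not support that. What stands is that the intention is unstated and that nothing records whether it was met.

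A reader might also infer that the associations will be confounded. That does not follow. The two recruitment routes and two locations make a link between timing and pain conceivable, but no section shows that timing differs between them.

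Three further limits are fair. The insulin-resistance assays are not named, so the point reaches only those that turn out to depend on fasting. Because saliva collection is not described, it cannot be shown that saliva is taken at the visit; faecal samples, for comparison, are collected at home. The models in Methods are worded around synovial fluid findings, and no cortisol or insulin-resistance model is written out, so the absent timing term is part of a wider lack of named covariates.

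Finally, the document is Version 4.2 of June 2022, and enrolment was planned to end in late summer 2022. New form fields may therefore cover only the remaining participants.

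**Conclusion.** The point holds as a cheap improvement to secondary, exploratory aims. As written, visit timing and recent food can add removable variance to salivary cortisol and to any fasting-dependent insulin-resistance marker, and the planned analysis does nothing to remove it. The expected effect is dilution. Confounding is a possibility that the plan could not check, not something the documents demonstrate.

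The size is unknown. The fall in power from 95% to 93–71% rests wholly on an assumed true correlation of 0.30 and an assumed 10–50% timing share, and one range is used for all markers although they may differ. If visits were in practice all fasted and in the morning, the timing share for blood markers would be small and the loss close to nil.

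A reader might extend the point to the primary objective on synovial fluid proteomic signatures, or to the pain score itself. Nothing in the documents shows that either is affected.

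**What to change.** - **Record** clock time and hours since last food or drink at every blood and saliva collection. For participants already seen, retrieve appointment times where they are available.
- **Model.** Force clock time into the cortisol models, and both clock time and hours since food into the insulin-resistance models. Do not leave them to backward stepwise selection, which could drop them.
- **Sensitivity analysis.** Report fasting-dependent indices in samples recorded as fasted.
- **Text.** Reconcile Participant Duration and Recruitment with the breakfast line in Study Regimen so that all three describe the same visit, and add the saliva collection step, with its timing, to Study Regimen.

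**Cost.** Two form fields and two model terms. In the illustration, two covariates replace √137 by √135 = 11.62, so power at r = 0.30 becomes Φ(0.3095 × 11.62 − 1.96) = 94.9%, provided that they capture the timing variance fully. The real costs are incomplete covariates for participants already enrolled and a smaller n for the fasted-only analysis.
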